1.1 Background

This project seeks to compare the clinical performance and subjective acceptance of the Biofinity Energys contact lens (CooperVision Inc.) when compared to single-vision spectacles in subjects who have never worn contact lenses and who use digital devices (phones, tablets, laptops, desktop computers) for at least 4 hours per day on at least 5 days per week.

1.3 Study objectives

The aim of this clinical work is to compare the clinical performance and subjective acceptance of Biofinity Energys (CooperVision Inc.) contact lens when compared to single-vision spectacles in subjects who use digital devices (phones, tablets, laptops, desktop computers) for at least 4 hours per day on at least 5 days per week. Seventy-six subjects will be randomised to use either their habitual spectacles or the study contact lenses for two months. Subjects will be asked to complete the Computer Vision Syndrome Questionnaire (CVS-Q) at each visit which is a validated 16-item questionnaire designed to measure visual symptoms related to the use of digital devices. The CVS-Q investigates both 'internal' (burning, itching, tearing, redness, dryness) and 'external' symptoms (e.g. eye pain, double vision, headache, blurred vision).

[REDACTED]

1.4 Study design

This will be a randomised, open label, parallel group study, in which 76 subjects will be randomised to either continue wearing their habitual spectacles, or the Biofinity Energys contact lens, for a period of two months.

1.5 Statistical considerations

[REDACTED]

[REDACTED] As such, these will be compared using linear regression models or other parametric methods. [REDACTED]

[REDACTED] Deviations

from this statistical plan will be discussed in the final report. Deviations may be necessary due to differences between the actual data distribution compared with the anticipated data distribution.

1.5.1 Power analysis

Using data from the literature and assuming a superiority study design, 34 subjects are required to use each treatment (contact lenses or spectacles) for 90% power, assuming a standard deviation of CVS-Q score of 4.0 units and a meaningful difference of score of 3.2 units (5% of the amplitude of the CVS-Q). To allow for discontinuations, 38 subjects will be randomised into each group, meaning 76 subjects in total.

1.6 Risk analysis

This study is considered to be a non-significant risk study based on United State Food and Drug administration (FDA) and International Standards Organization (ISO) guidelines due to the daily wear nature of the study. With the potential benefit of this study, the work is considered to be ethically justifiable. Ethical approval will be sought from the University of Manchester Senate Committee on the Ethics of Research on Human Beings (hereafter referred to as Manchester UREC). The work where practical will be conducted in accordance with the ICH Good Clinical Practice Guidelines and the international standard BS EN ISO 14155:2011 'Clinical investigation of medical devices for human subjects'.

Section 2. Resources

2.1 Subject selection

In this work 76 subjects will be recruited.

2.1.1 Subject withdrawal and replacement

This study includes up to four clinical visits. Once the study consent form is signed, the subject is considered to be enrolled on the study. Subjects who have signed the consent form, but who have not completed the dispensing visit will usually be replaced. All subject data will be included in the final analyses unless there are strong grounds for exclusion; such grounds will be detailed in the final report. At the end the study, all subjects will sign a study exit form.

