3.1 Visit scheduling

Subjects will be required to attend up to four study visits (three, in the case of the spectacle group). Acceptable date ranges are shown in Table 3. Subjects in the contact lens group may need to attend for more than one 'teach' session.

| Visit | Target | Allowable range |
|------------------------------|----------------------------|-------------------------------|
| Initial visit | N/A | N/A |
| 2 week visit (CL group only) | 14 days from initial visit | 10-20 days from initial visit |
| 1 month visit | 30 days from initial visit | 25-35 days from initial visit |
| 2 month visit | 30 days from 1 month visit | 25-35 days from 1 month visit |

Table 3: Visits and allowable ranges.

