3.1.2 Missed visits

Subjects not attending for a visit will be contacted and encouraged to return for assessment. If two consecutive study visits are missed, the subject will be discontinued. It is expected that Eurolens Research personnel will attempt all reasonable means of communication in this event, including corresponding with the subject by letter.

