3.2.2 Initial visit

Subjects should attend this visit wearing (or having brought along) the spectacles that they use for digital device use (the visit cannot go ahead if they do not bring their spectacles). They will then be required to sign an informed consent form prior to

enrolment [REDACTED] A copy of the signed form will be issued to the subject. When the subject has signed the consent form, they are considered to be enrolled on the study.

Subjects will be instructed on the following:

- Lens handling, application and removal, where necessary.
- Use of multipurpose care regimen, where necessary.
- Specific study instructions, such as the importance of not using any other contact lens products.
- General information such as the management of red eyes.

The following procedures will be performed (any ocular measurement procedures outlined below will be carried out on each eye):

1. Details of the ocular history of the subject will be noted (including habitual spectacle details and wear time) This will include recording details about the spectacles to ensure the same pair are worn for the entire study.
2. Details of general health and medications will be recorded.
3. [REDACTED]
4. The CVS-Q questionnaire will be completed.
5. [REDACTED]
6. The BVD of the subject's spectacles will be recorded by asking the subject to position the spectacles on their own face (if not already being worn).
7. Focimetry will be carried out on the subject's spectacles to ascertain the prescription of the lenses.
8. [REDACTED]
[REDACTED]
[REDACTED]
[REDACTED]
[REDACTED]
9. [REDACTED]
[REDACTED]
[REDACTED]
10. [REDACTED]
[REDACTED]
11. [REDACTED]
[REDACTED]
[REDACTED]
[REDACTED]

- [REDACTED]
- [REDACTED]

12. [REDACTED]
[REDACTED]
[REDACTED]
[REDACTED]
[REDACTED]
[REDACTED]
[REDACTED]

[REDACTED]

The presence of any ocular adverse events will be recorded [REDACTED]

13. The investigator will confirm that the subject satisfies all the inclusion and exclusion criteria. Subjects who fail to meet all the criteria at this time will usually be discontinued and replaced. If in the opinion of the investigator, the subject may be eligible at a later date, the subject may be brought back for up to ONE repeat visit of this type.

14. The subject will be randomised to one of the two treatment groups. The spectacle wearers will be discharged from the study visit at this point, and asked to return for the one-month visit. [REDACTED]

[REDACTED]
[REDACTED]
[REDACTED]

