15. For those assigned to the contact lens group, the study lenses will be fitted and allowed to settle for five minutes or until tearing stops (whichever is the longer).

16. [REDACTED]
[REDACTED]
[REDACTED]
[REDACTED]

[REDACTED]

17. [REDACTED]

18. [REDACTED]

- I [REDACTED]
- I [REDACTED]
- I [REDACTED]

19. [REDACTED]

21. Subjects will be trained on contact lens application, removal, solution use and best practice immediately at the end of this visit or at a later date if required. More than one visit is possible for this 'teaching' session if they have problems with handling. Subjects will be dispensed with contact lenses and solution only once the Investigator is satisfied with their ability to successfully apply and remove the lenses.

22. Subjects will be discharged and asked to return for a two-week follow-up visit wearing the Biofinity Energys contact lenses, [REDACTED]

[REDACTED]

No formal 'building up' of wearing time will take place, [REDACTED]

[REDACTED]

Some subjects

may achieve this on the first day of wear, others may take a few days before they are happy to wear for 8 hours, but all subjects should progress to a minimum of 8 hours per day as soon as they are able. Subjects will also be asked to bring their lens case to the follow-up visit.

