3.2.4 Visit 3: One month visit

For the contact lens group, subjects should attend wearing their Biofinity lenses which should have been in situ for at least 2 hours. Subjects who attend without lenses in situ for at least 2 hours will usually be rescheduled.

For the spectacle group, subjects should attend wearing (or having brought with them) the spectacles that they have been wearing for digital device use. Spectacles should have been worn for a minimum of 2 hours on the day of the visit.

For the contact lens group, this visit will be identical to the two week visit except that the contact lenses will be discarded at the end of the visit and they will be provided with a new pair of lenses.

For the spectacle group, the following will take place:

1. Any medical or ocular issues since the last visit will be recorded.
2. Spectacle wearing times since the previous visit will be recorded (hours per day, days per week and comfortable hours per day).
3. [REDACTED]
4. [REDACTED]
5. The CVS-Q questionnaire will be completed.
6. [REDACTED]

7. [REDACTED]
8. The subject will be discharged and asked to return for the two month visit wearing their spectacles. Subjects should be asked to wear their spectacles for a minimum of eight hours per day, five days per week, and whilst using digital devices for at least four hours per day.

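### The replacement rule in 2.1.1 runs past randomisation, where it can reach only the lens arm, and lens subjects who are never dispensed may have no 1- and 2-month CVS-Q

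*Combined protocol and SAP*

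**What the plan says.** **Replacement.** Section 2.1.1: "Subjects who have signed the consent form, but who have not completed the dispensing visit will usually be replaced". The dispensing visit is not defined in the visible text and is not a row of Table 3. The same section keeps all subjects' data in the final analyses unless there are strong grounds for exclusion.

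**Numbers.** Section 1.5.1: "To allow for discontinuations, 38 subjects will be randomised into each group", 76 in total.

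**Order of events (3.2.2).** The CVS-Q is step 4, confirmation of eligibility step 13 and randomisation step 14. On the spectacle arm, step 14 adds: "The spectacle wearers will be discharged from the study visit at this point". Lens fitting is step 15. Step 21 makes dispensing conditional on handling skill: "Subjects will be dispensed with contact lenses and solution only once the Investigator is satisfied with their ability". Training may take place on a later day, and section 3.1 adds: "Subjects in the contact lens group may need to attend for more than one 'teach' session".

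**Follow-up.** Section 1.3 has the CVS-Q completed at every visit. For the lens group at 1 month, section 3.2.4 says: "Subjects who attend without lenses in situ for at least 2 hours will usually be rescheduled". The 2-week visit carries the same condition, and section 3.2.5 makes the 2-month visit identical to the 1-month visit. On non-attendance, section 3.1.2 says: "Subjects not attending for a visit will be contacted and encouraged to return for assessment".

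**The concern.** The replacement window is tied to dispensing, but the arms part at randomisation, which comes first. A subject can be randomised to lenses, fail to master handling, never be dispensed, and still fall within the words of 2.1.1. A spectacle subject has no matching step.

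Two things follow. First, each such replacement adds a subject to the lens arm beyond the number in 1.5.1. Second, and more important for the result, no visible text says how an undispensed lens subject is followed up, and the lens-arm visits are written for people wearing lenses. If those subjects have no later CVS-Q, the lens arm is selected after randomisation on ability to handle lenses, and the spectacle arm is not. If ability to handle lenses is related to CVS-Q score, the between-group difference is biased.

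**Working it through.** **1. The plan's own figure.** Inputs from 1.5.1: SD 4.0, difference 3.2, power 90%. Two-sided 5% is assumed, because the visible text states no alpha. For a two-sample t test with n per arm, the noncentrality is 3.2 / (4.0 × √(2/n)).
- n = 34: noncentrality 3.30, power 0.9015.
- n = 33: power 0.8926.

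So 34 per group reproduces. The allowance is 38 − 34 = 4 per group, and 4/38 = 10.5%.

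**2. Whom the replacement rule can reach.**
- Consent to step 13: both future arms, not yet randomised.
- Step 14: randomisation; spectacle subjects leave.
- Steps 15 to 21: lens arm only, already randomised, not yet dispensed.

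If k lens subjects are replaced in the last window, the lens arm becomes 38 + k and the total 76 + k. For example, k = 4 gives 42 and 80.

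**3. Is power the problem?** No. If 4 undispensed lens subjects are not replaced and have no outcome, the comparison is 34 against 38 and power is 0.917. Replacement is not needed to protect the 90%.

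**4. Possible bias if their outcomes are missing.** Let q be the share of the lens arm never dispensed, and g the amount by which they would score worse on the CVS-Q than dispensed subjects. Neither is in the documents; both are assumed. The full lens-arm mean is (1 − q) × dispensed mean + q × undispensed mean, so leaving the undispensed out shifts the mean by q × g in favour of lenses. The probability of falsely favouring lenses when the true difference is zero is taken from the noncentral t (34 per arm, SD 4.0, two-sided 5%, unadjusted):

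| q | g | Bias = q × g | P(falsely favour lenses) |
|---|---|---|---|
| any | 0 | 0 | 0.0250 |
| 5% | 2 | 0.10 | 0.0316 |
| 10% | 2 | 0.20 | 0.0395 |
| 10.5% | 4 | 0.42 | 0.0626 |

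The last row uses the whole discontinuation allowance and a gap of one SD. Its bias is 0.42/3.2 = 13% of the target difference. A negative g gives the same figures in favour of spectacles.

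**5. Power if undispensed subjects are kept in the lens arm.** Assume a share p is undispensed and gains nothing, while dispensed subjects gain 3.2. The effect is then 3.2 × (1 − p) and the lens-arm variance 16 + 3.2² × p(1 − p). With 38 per arm:
- p = 5%: effect 3.04, variance 16.49, power 0.901.
- p = 10%: effect 2.88, variance 16.92, power 0.863.

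**The case against.** The case for leaving the text alone is fair in several respects.

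- **The conflict may never arise.** Section 2.1.1 says usually, and step 13 uses similar wording for eligibility failures before randomisation. A reader might infer that 2.1.1 flatly contradicts 1.5.1. It does not: a conflict needs a randomised lens subject who is not dispensed and is then replaced. The ambiguity remains, though. Step 13 and section 2.2 already cover ineligible subjects, and 2.1.1 sets its own end point at dispensing.
- **Replacement does not discard data.** This stands. Any bias comes through the uncollected outcome.
- **The spectacle arm loses people too.** A reader might infer that it keeps everyone. Section 2.2 discontinuation applies to both arms, and 1.5.1 allows for losses in each. Only loss at dispensing is confined to lenses.
- **The missed-visit rule.** Section 3.1.2 says: "If two consecutive study visits are missed, the subject will be discontinued". A reader might infer that an undispensed subject is removed this way before 2 months. That requires visits attended or postponed without lenses to count as missed, which is not stated. The visible text speaks of rescheduling and of encouraging return, and nothing visible forbids taking a CVS-Q without lenses.
- **Redaction.** Most of 1.5, text after step 14, steps 16 to 19 and part of step 22 are blacked out. A follow-up rule or analysis set may be there, so its absence from the plan is not shown.
- **Interest in users.** Section 1.5.1 sizes the trial on subjects who use each treatment, so an analysis of dispensed subjects has a place. It fits best as a sensitivity analysis, because it gives up the comparison that randomisation protects.

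**Conclusion.** The point holds as a modest one. On the visible text the replacement window extends past randomisation and from there can apply only to the lens arm. The lens-arm visit conditions are ones that an undispensed subject cannot meet. Whether this leads to over-recruitment or to missing outcomes depends on how staff apply the rule and on redacted text.

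The figures in the working are illustrations, resting on an assumed q and g, two-sided 5% and no baseline adjustment; zero bias is within the range and the direction could reverse. A reader might quote 12.6% for a false result in favour of lenses. That needs q = 20%, about twice the trial's entire allowance, together with a gap of 4 units, and nothing in the documents supports that pair. Requiring willingness to be fitted (2.1.3) and allowing repeat training both suggest that few subjects would go undispensed.

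This is a cheap improvement of minor to moderate severity. The sample size of 34, raised to 38, is not in question.

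**What to change.** 1. In 2.1.1, state that replacement applies only before randomisation (step 14), drop the undefined dispensing visit as the end point, and count every randomised subject toward the 76.
2. Unless redacted text already provides for it, add to 3.2.4 and 3.2.5 that lens-arm subjects who are never dispensed are asked for the CVS-Q at 1 and 2 months, with the lens-wear condition waived for that questionnaire.
3. Analyse them in the lens arm, in line with the data-inclusion rule in 2.1.1, and add a dispensed-only sensitivity analysis.
4. Report how many subjects were randomised to lenses but never dispensed, and compare their step-4 baseline CVS-Q with that of dispensed lens subjects. Sections 2.2 and 3.4 record discontinuations and numbers analysed but do not separate this group.

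The cost is a few sentences, a few extra questionnaires and some dilution. If undispensed subjects gain nothing, power with 38 per arm stays at about 90% when 5% are undispensed and falls to about 86% at 10%, before other losses. If the redacted text already covers items 2 to 4, only the wording of 2.1.1 needs to change.

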2.1.2 Subject recruitment

Subjects will be recruited by one or more of following means:

1. Posting study details on The University of Manchester's 'Research Volunteers' website.
2. Correspondence to existing wearers on the Eurolens Research database of subjects.
3. Advertising through a variety of media via a format separately approved by Manchester UREC.

2.1.3 Inclusion criteria

Subjects will only be eligible for the study if:

1. They are between 18 and 35 years of age (inclusive).
2. They understand their rights as a research subject and are willing and able to sign a Statement of Informed Consent.
3. They are willing and able to follow the protocol.
4. They are a 'neophyte' (i.e. someone who has not worn contact lenses previously, with the exception for the purposes of a trial fitting, lasting up to one week).
5. They have a contact lens spherical prescription between -1.00 to -6.25D (inclusive) based on the ocular refraction.
6. They have a cylindrical correction of -0.875DC or less in each eye based on the ocular refraction
7. They own and habitually wear single vision spectacles used for both distance and near vision, including computer and digital device use.

8. Their single vision spectacles have a mean sphere equivalent within $\pm 0.50D$ of that of the refraction found in the study for each eye (after having taken lens effectivity into account).
9. They are willing to be fitted with contact lenses and understand they may be randomised to either group.
10. They are willing to wear the contact lenses (if relevant) or spectacles for at least 8 hours per day, 5 days per week.
11. They typically use digital devices for a minimum of 4 hours per day, 5 days per week.
12. They agree not to change the spectacles they will wear for digital device use for the duration of the study.
13. They agree not to participate in other clinical research for the duration of the study.

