2.6.1 Lenses

Details of the study lenses are provided in Table 2. The lens is CE marked. Initial lens selection will be as indicated by the manufacturer fitting guidelines.

| | |
|----------------------|---------------------------------|
| Name | Biofinity Energys |
| Manufacturer | CooperVision Inc. |
| Material | comfilcon A |
| EWC (%) | 48 |
| BOZR (mm) | 8.6 |
| Diameter (mm) | 14.0 |
| Spherical powers (D) | -0.50 to - 6.00 (0.25 steps) |

Table 2: Study lenses.

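### Inclusion criterion 5 admits contact lens prescriptions up to -6.25D, but the only study lens is listed up to -6.00D

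*Combined protocol and SAP*

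**What the plan says.** Criterion 5 in section 2.1.3 sets the refractive range for entry: "They have a contact lens spherical prescription between -1.00 to -6.25D (inclusive) based on the ocular refraction". Criterion 6 adds a limit on astigmatism: "They have a cylindrical correction of -0.875DC or less in each eye based on the ocular refraction".

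Table 2 in section 2.6.1 describes one lens, Biofinity Energys, and gives its spherical powers (all minus) as "0.50 to - 6.00 (0.25 steps"). Section 1.4 confirms that this is the only contact lens in the design; the other group keeps its habitual spectacles. On choice of power, section 2.6.1 says "Initial lens selection will be as indicated by the manufacturer fitting guidelines". Those guidelines are not reproduced.

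Section 3.2.2 sets the order of events at the initial visit:

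- Step 13: "The investigator will confirm that the subject satisfies all the inclusion and exclusion criteria".
- Step 14: "The subject will be randomised to one of the two treatment groups".
- Step 15: "For those assigned to the contact lens group, the study lenses will be fitted and allowed to settle for five minutes".

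Section 2.1.1 covers subjects who drop out early: "Subjects who have signed the consent form, but who have not completed the dispensing visit will usually be replaced".

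**The concern.** The eligibility limit runs one step past the listed lens supply. An investigator applying criterion 5 as written would accept a subject at -6.25D. If that subject were allocated to lenses, Table 2 would offer no lens of that power.

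If nothing outside the visible text deals with this, two outcomes are possible. The subject could be fitted 0.25D short of the prescription. Or the subject could be lost before dispensing is complete and replaced under section 2.1.1. For this reason, replacement could arise only in the lens group, because spectacle subjects need no lens power. A post-randomisation loss that can happen in one group only is best prevented before allocation, even when the numbers are small. The visible text does not establish that either outcome would occur.

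**Working it through.** **Inputs**

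- Eligible contact lens sphere: -1.00D to -6.25D inclusive (section 2.1.3, criterion 5).
- Listed lens powers: -0.50D to -6.00D in 0.25D steps (section 2.6.1, Table 2).
- Subjects randomised to lenses: 38 (section 1.5.1).
- Distribution of prescriptions: not given. An even spread over the eligible range is assumed for illustration.

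**Comparing the two ranges**

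- Eligible quarter-dioptre values: (6.25 - 1.00)/0.25 + 1 = 22.
- Listed powers: (6.00 - 0.50)/0.25 + 1 = 23.
- Eligible values with a listed power: (6.00 - 1.00)/0.25 + 1 = 21.
- Eligible values without one: 22 - 21 = 1, namely -6.25D.
- Size of the gap: 6.25 - 6.00 = 0.25D. At the other end, -1.00D is covered.

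**Does vertex distance explain it?** No. Criterion 5 is already stated as a contact lens prescription based on the ocular refraction, so no further vertex correction is due that would bring -6.25D to -6.00D.

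**How many subjects could be affected?** The count is of subjects with at least one eye affected, which assumes that criterion 5 applies to each eye. Criterion 6 says so for cylinder; criterion 5 does not. Two forms of the even spread are used:

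- *Stepped*: prescriptions fall on the 22 quarter-dioptre values. The share per eye is 1/22 = 4.5%.
- *Continuous*: the sphere takes any value and is rounded to the nearest 0.25D, so values beyond -6.125D round to -6.25D. The share per eye is (6.25 - 6.125)/(6.25 - 1.00) = 0.125/5.25 = 2.4%.

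If the two eyes are alike, the share of subjects equals the share per eye, p. If they are independent, it is 1 - (1 - p)².

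| Assumption | Share of subjects | Expected of 38 |
|---|---|---|
| Continuous, eyes alike | 0.125/5.25 = 2.4% | 0.9 |
| Continuous, eyes independent | 1 - (1 - 0.0238)² = 4.7% | 1.8 |
| Stepped, eyes alike | 1/22 = 4.5% | 1.7 |
| Stepped, eyes independent | 1 - (21/22)² = 8.9% | 3.4 |

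The cylinder limit of -0.875DC is not a quarter step, which suggests that the continuous rows may fit better. All four figures fall if prescriptions near the limit are rarer than an even spread implies.

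**Sample size.** The 34 per group in section 1.5.1 does not depend on this point. It is reproduced by a two-sample t-test with SD 4.0, difference 3.2, 90% power and an assumed two-sided 5% level: 33.8, rounded up to 34. Neither that figure nor the 38 per group and 76 in total changes.

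**The case against.** The two figures describe different things: a subject's prescription and a list of stocked powers. They conflict only if the lens must match the prescription exactly, and no visible text requires that. Lens selection is left to guidelines that cannot be seen here, and a limit one step past the range is compatible with a deliberate tolerance. The design also accepts larger errors elsewhere: criterion 8 lets habitual spectacles differ from the study refraction by up to 0.50D mean sphere, twice the gap at issue, and criterion 6 admits cylinder although Table 2 lists spherical powers only. Much of section 3.2.2 around eligibility and fitting is redacted (steps 8 to 12, text after the randomisation sentence in step 14, and steps 16 to 19), and a rule on lens power could sit there. Criterion 3, on being able to follow the protocol, might also be used to screen out a subject who cannot be supplied. Finally, the percentages rest on an assumed even spread, and the highest also treats a person's two eyes as independent.

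Most of this stands as a limit on size. A 0.25D shortfall is small by the protocol's own standards, the consequences are not established, and the percentages are illustrative. None of it makes the two visible figures agree. Criterion 5 mentions no tolerance and points to no rule elsewhere, and criterion 3 says nothing about lens powers. The section 2.2 provision for replacing subjects who fail the criteria does not reach someone who meets criterion 5.

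**Conclusion.** The mismatch is real and certain: one 0.25D step, at the -6.25D end only, between an eligibility limit applied before randomisation and the listed powers of the only study lens. High confidence applies to that mismatch alone. Whether any subject would be fitted short or lost depends on redacted text and on guidelines outside the documents. The illustrative range of 0.9 to 3.4 lens subjects rests on the even spread and on reading criterion 5 per eye. The point is minor, with no claimed effect on power, bias or the analysis.

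**What to change.** Reconcile criterion 5 with Table 2, with the sponsor deciding which of the two is in error. The result should be that every subject confirmed eligible at step 13 can be supplied from the listed powers in both eyes before randomisation at step 14. If a tolerance is intended, or a redacted step or the fitting guidelines already covers the case, criterion 5 should say so and refer to it.

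The cost is a one-line amendment. If Table 2 is corrected, or an existing tolerance is stated, no eligible subject is lost. If criterion 5 is changed, the pool of eligible subjects shrinks slightly, by 2.4% to 8.9% under the same even-spread assumption.
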